5.3 Lifestyle Considerations

5.3.1 Meals and Dietary Restrictions

Participants should maintain a normal diet unless modifications are required to manage an AE such as diarrhea, nausea, or vomiting.

5.3.2 Caffeine, Alcohol, and Tobacco Restrictions

None.

5.3.3 Activity Restrictions

None.

5.3.4 Contraception

Pembrolizumab may have adverse effects on a fetus in utero. Refer to Appendix 5 for approved methods of contraception.

Participants should be informed that taking the study medication may involve unknown risks to the fetus (unborn baby) if pregnancy were to occur during the study. In order to participate in the study, participants of childbearing potential must adhere to the contraception requirement (Appendix 5) from the day of study medication initiation (or 14 days prior to the initiation of study medication for oral contraception) throughout the study period up to 120 days after the last dose of study medication. If there is any question that a participant of childbearing potential will not reliably comply with the requirements for contraception, that participant should not be entered into the study.

5.3.5 Pregnancy

If a participant inadvertently becomes pregnant while on treatment with pembrolizumab, the participant will be immediately discontinued from study intervention. The site will contact the participant at least monthly and document the participant's status until the pregnancy has been completed or terminated. The outcome of the pregnancy will be reported to the Sponsor without delay and within 24 hours if the outcome is a serious adverse experience (eg, death, abortion, congenital anomaly, or other disabling or life-threatening complication to the mother or newborn). The study Investigator will make every effort to obtain permission to follow the outcome of the pregnancy and report the condition of the fetus or newborn to the Sponsor. If a male participant impregnates his female partner, the study personnel at the site must be informed immediately and the pregnancy must be reported to the Sponsor and followed as described in Section 8.4.

5.3.6 Use in Nursing Women

It is unknown whether pembrolizumab is excreted in human milk. Since many drugs are excreted in human milk, and because of the potential for serious adverse reactions in the nursing infant, participants who are breastfeeding are not eligible for enrollment.

5.4 Screen Failures

Screen failures are defined as participants who consent to participate in the clinical study, but are not subsequently randomized in the study. A minimal set of screen failure information is required to ensure transparent reporting of screen failure participants to meet the Consolidated Standards of Reporting Trials (CONSORT) publishing requirements and to respond to queries from regulatory authorities. Minimal information includes demography, screen failure details, eligibility criteria, and any AEs or SAEs meeting reporting requirements as outlined in the data entry guidelines. Re-screening is allowed in the study (see Section 8.1.9).

5.5 Participant Replacement Strategy

A participant who discontinues from study intervention OR withdraws from the study will not be replaced.

6 STUDY INTERVENTION

Study intervention is defined as any investigational intervention(s), marketed product(s), placebo, or medical device(s) intended to be administered to a study participant according to the study protocol.

Clinical supplies (study interventions of V937 and pembrolizumab provided by the Sponsor) will be packaged to support enrollment. Clinical supplies will be affixed with a clinical label in accordance with regulatory requirements.

6.1 Study Intervention(s) Administered

The study intervention(s) to be used in this study are outlined in [Table 7](#).

Country-specific differences are noted in Appendix 7.

Table 7 Study Interventions

Arm Name	Arm Type	Intervention Name	Type	Dose Formulation	Unit Dose Strength(s)	Dosage Level(s)	Route of Administration	Regimen/ Treatment Period/ Vaccination Regimen	Use	IMP or NIMP/ AxMP	Sourcing
Arm 1	Experimental	Pembrolizumab	Biological/ Vaccine	Solution for Infusion	25 mg/mL	200 mg	IV Infusion	Day 8 of Cycle 1 (28-day cycle)	Test Product	IMP	Provided centrally by Sponsor
Arm 1	Experimental	V937	Biological/ Vaccine	Solution for Infusion	7.5 X 10 ⁷ TCID50/ mL	1 X 10 ⁹ TCID50	IV Infusion	Day 1 of each subsequent 21-day cycle Days 1, 3, 5, and 8 of Cycle 1 (28-day cycle) Day 1 of Cycles 2-8 (21-day cycles)	Test Product	IMP	Provided centrally by Sponsor
Arm 2	Experimental	Pembrolizumab	Biological/ Vaccine	Solution for Infusion	25 mg/mL	200 mg	IV Infusion	Day 8 of Cycle 1 (28-day cycle) Day 1 of each subsequent 21-day cycle	Test Product	IMP	Provided centrally by Sponsor

Arm Name	Arm Type	Intervention Name	Type	Dose Formulation	Unit Dose Strength(s)	Dosage Level(s)	Route of Administration	Regimen/ Treatment Period/ Vaccination Regimen	Use	IMP or NIMP/ AxMP	Sourcing
Arm 2	Experimental	V937	Biological/ Vaccine	Solution for Injection	7.5 X 10 ⁷ TCID ₅₀ / mL	3 X 10 ⁸ TCID ₅₀	Intra-tumoral	Days 1, 3, 5, and 8 of Cycle 1 (28-day cycle) Day 1 of Cycles 2-8 (21-day cycles)	Test Product	IMP	Provided centrally by Sponsor
Arm 3	Experimental	Pembrolizumab	Biological/ Vaccine	Solution for Infusion	25 mg/mL	200 mg	IV Infusion	Day 8 of Cycle 1 (28-day cycle) Day 1 of each subsequent 21-day cycle	SoC	IMP	Provided centrally by Sponsor

Note: V937 will be administered 0.5 to 4 h after pembrolizumab infusion (as appropriate).

The classification of IMP and NIMP/AxMP is based on guidance issued by the European Commission and applies to countries in the EEA. Regional and/or Country differences of the definition of IMP and NIMP/AxMP may exist. In these circumstances, local legislation is followed.

EEA=European Economic Area; IMP=Investigational Medicinal Product; IV=intravenous; NIMP/AxMP=Noninvestigational/Auxiliary Medicinal Product; SoC=standard of care; TCID₅₀=50% tissue culture infectious dose.

All study interventions will be administered on an outpatient basis.

All products indicated in [Table 7](#) will be provided centrally by the Sponsor.

For any commercially available product that is provided by the study site, subsidiary, or designee, every attempt will be made to source these supplies from a single lot/batch number. The study site is responsible for recording the lot number, manufacturer, and expiry date for any locally purchased product as per local guidelines unless otherwise instructed by the Sponsor.

Refer to Section 8.1.10 for details regarding administration of the study intervention.

6.1.1 Administration of Pembrolizumab

A 200-mg dose of pembrolizumab will be infused over 30 minutes. In Arms 1 and 2, pembrolizumab administration will be 0.5 to 4 hours prior to V937 administration. For administration details, see Pharmacy Manual.

6.1.2 Administration of V937 (Arms 1 and 2)

6.1.2.1 Administration of V937 in Arm 1

In Arm 1, V937 will be infused IV over 30 minutes. For Cycles 2-8, V937 administration will occur 0.5 to 4 hours after a 200-mg dose of pembrolizumab infused over 30 minutes. For administration details, see the Pharmacy Manual.

6.1.2.2 Administration of V937 in Arm 2

In Arm 2 of the study, V937 will be administered by ITu injection into cutaneous, subcutaneous, and/or nodal lesions that are visible, palpable, or detectable by ultrasound guidance. V937 will be administered with a total maximal volume of injectate of 4 mL per treatment visit for all injected lesions combined. **A maximum of 5 lesions can be injected per visit.**

V937 administration will occur 0.5 to 4 hours after a 200-mg dose of pembrolizumab infused over 30 minutes.

Each participant will receive V937 in a volume of 0.5 to 4 mL of injectate. The amount of V937 administered will depend on the number of lesions injected and the size of those lesions. See [Table 8](#) for dose-level range. The volume of injectate delivered to each lesion will be based on the longest dimension of the target lesion as shown in [Table 8](#) (short axis diameter in the case of lymph nodes), and on the number of lesions injected. Documentation of dose volume administered per lesion will be obtained.

Prioritization of lesions to be injected should include consideration of the following order:

First: New or progressing lesion(s)

Second: The largest lesion(s)

If multiple lesions exist, a new or progressing lesion should be considered for injection first, followed by injection of the largest lesion, then injection of any additional lesions, up to a total volume of injectate of 4 mL and a maximum number of 5 lesions.

The total volume administered to all lesions can range from 0.5 to 4 mL per participant, per visit. Distant lesion(s) assessed for the “abscopal” response should not be injected, unless approved by the Sponsor.

Table 8 Determination of Minimum Target Lesion Diameter at Treatment Initiation by Dose Level

Target Lesion Size (longest dimension)	Injection Volume ^a
>2.5 cm	2 mL
1.5 to 2.5 cm	1 mL
0.5 to <1.5 cm	0.5 mL

^a Volumes are estimates; total volume injected per visit for all tumor lesions combined = 4 mL.

Details on dose calculation, preparation, and administration of V937 are provided in the Procedures Manual.

Injected tumor area should consist of vital tumor tissue (avoid injection into areas with significant necrosis, if feasible). The injected, single, sufficiently-sized target lesion at treatment initiation should be the same lesion that underwent pretreatment biopsy.

If at any time after treatment initiation a dose cannot be fully injected into the single target lesion identified at the start of treatment (eg, due to tissue induration or tumor shrinkage), the dose may be split and the remaining amount of V937 may be injected into another accessible target lesion(s). Documentation of dose volume administered per target lesion should be obtained. If no other target lesion is accessible for injection or lesions are no longer visible, the remaining amount may alternatively be injected subcutaneously into the tissue immediately surrounding the target lesion, if assessed feasible by the treating physician. Site and volume for each injection must be documented in the electronic case report form (eCRF).

6.2 Preparation/Handling/Storage/Accountability

6.2.1 Dose Preparation

Details on preparation and administration of V937 and pembrolizumab are provided in the Pharmacy Manual.

There are no specific calculations or evaluations required to be performed in order to administer the proper dose to each participant. The rationale for selection of doses to be used in this study is provided in Section 4.3.

6.2.2 Handling, Storage, and Accountability

The investigator or designee must confirm appropriate temperature conditions have been maintained during transit for all study intervention received, and any discrepancies are reported and resolved before use of the study intervention.

Only participants enrolled in the study may receive study intervention, and only authorized site staff may supply or administer study intervention. All study interventions must be stored in a secure, environmentally controlled, and monitored (manual or automated) area in accordance with the labeled storage conditions with access limited to the investigator and authorized site staff.

The investigator, institution, or the head of the medical institution (where applicable) is responsible for study intervention accountability, reconciliation, and record maintenance (ie, receipt, reconciliation, and final disposition records).

For all study sites, the local country Sponsor personnel or designee will provide appropriate documentation that must be completed for drug accountability and return, or local discard and destruction if appropriate. Where local discard and destruction is appropriate, the investigator is responsible for ensuring that a local discard/destruction procedure is documented.

The study site is responsible for recording the lot number, manufacturer, and expiry date for any locally purchased product (if applicable) as per local guidelines unless otherwise instructed by the Sponsor.

The investigator shall take responsibility for and shall take all steps to maintain appropriate records and ensure appropriate supply, storage, handling, distribution, and usage of study interventions in accordance with the protocol and any applicable laws and regulations.

6.3 Measures to Minimize Bias: Randomization and Blinding

6.3.1 Intervention Assignment

Participants will be randomized centrally using an interactive voice response system/integrated web response system (IVRS/IWRS). Participants will be randomly assigned in a 1:1:1 ratio to the following intervention arms: Arm 1 (IV pembro + IV V937); Arm 2 (IV pembro + ITu V937); Arm 3 (IV pembro alone).

6.3.2 Stratification

Intervention allocation/randomization will be stratified according to the following factor:

(M1c+M1d) versus others, according to AJCC Cancer Staging Manual, Eighth Edition

6.3.3 Blinding

This is an open-label study; therefore, the Sponsor, investigator, and participant will know the intervention administered.

6.4 Study Intervention Compliance

Interruptions from the protocol-specified treatment plan for more than 12 weeks between pembrolizumab doses for non-drug-related or administrative reasons require consultation between the investigator and the Sponsor and written documentation of the collaborative decision on participant management.

Interruptions from the protocol-specified treatment plan for >12 weeks between V937 doses require consultation between the investigator and the Sponsor and written documentation of the collaborative decision on participant management.

6.5 Concomitant Therapy

Medications or vaccinations specifically prohibited in the exclusion criteria are not allowed during the ongoing study. If there is a clinical indication for any medication or vaccination specifically prohibited, discontinuation from study therapy or vaccination may be required. The investigator should discuss any questions regarding this with the Sponsor's Clinical Director. The final decision on any supportive therapy or vaccination rests with the investigator and/or the participant's primary physician. However, the decision to continue the participant on study intervention requires the mutual agreement of the investigator, the Sponsor, and the participant.

6.5.1 Acceptable Concomitant Medications

All treatments that the investigator considers necessary for a participant's welfare may be administered at the discretion of the investigator in keeping with the community standards of medical care except for those that are prohibited as described in Section 6.5.2. All concomitant medication will be recorded on the eCRF including all prescription, over-the-counter (OTC), herbal supplements, and IV medications and fluids. If changes occur during the study period, documentation of drug dosage, frequency, route, and date may also be included on the eCRF.

All concomitant medications received within 28 days prior to the first dose of study intervention and 30 days after the last dose of study intervention should be recorded. If participants experience an SAE or ECI, all concomitant medications administered after 30 days after the last dose of study intervention are to be recorded for SAEs and events of clinical interest (ECIs) as defined in Section 8.4.7.

6.5.2 Prohibited Concomitant Medications

Participants are prohibited from receiving the following therapies during the Screening and Treatment Phases of this study:

- Antineoplastic systemic chemotherapy or biological therapy

- Immunotherapy not specified in this protocol
- Chemotherapy not specified in this protocol
- Investigational agents other than pembrolizumab
- Radiation therapy
Note: Radiation therapy to a symptomatic solitary lesion or to the brain may be allowed at the investigator's discretion.
- Live vaccines within 30 days prior to the first dose of study intervention and while participating in the study. Examples of live vaccines include, but are not limited to, the following: measles, mumps, rubella, varicella/zoster, yellow fever, rabies, BCG, and typhoid vaccine. Seasonal influenza vaccines for injection are generally killed virus vaccines and are allowed; however, intranasal influenza vaccines (eg, FluMist[®]) are live attenuated vaccines and are not allowed. (Refer local regulation in Appendix 7)
- Systemic glucocorticoids for any purpose other than to modulate symptoms from an AE that is suspected to have an immunologic etiology. The use of physiologic doses of corticosteroids may be approved after consultation with the Sponsor.

Participants who, in the assessment of the Investigator, require the use of any of the aforementioned treatments for clinical management should be removed from treatment. Participants may receive other medications that the investigator deems to be medically necessary.

6.5.3 Rescue Medications and Supportive Care

6.5.3.1 V937 Supportive Care

Participants should receive appropriate supportive care measures as deemed necessary by the treating investigator.

6.5.3.2 Pembrolizumab Supportive Care

Participants should receive appropriate supportive care measures as deemed necessary by the treating investigator. Suggested supportive care measures for the management of AEs with potential immunologic etiology are outlined along with the dose modification guidelines in Section 6.6, [Table 9](#). Where appropriate, these guidelines include the use of oral or IV treatment with corticosteroids, as well as additional anti-inflammatory agents if symptoms do not improve with administration of corticosteroids. Note that several courses of steroid tapering may be necessary as symptoms may worsen when the steroid dose is decreased. For each disorder, attempts should be made to rule out other causes such as metastatic disease or bacterial or viral infection, which might require additional supportive care. The treatment guidelines are intended to be applied when the investigator determines the events to be related to pembrolizumab.

Note: If after the evaluation of the event, it is determined not to be related to pembrolizumab, the investigator does not need to follow the treatment guidance. Refer to [Table 9](#) in Section 6.6 for guidelines regarding dose modification and supportive care.

It may be necessary to perform conditional procedures such as bronchoscopy, endoscopy, or skin photography as part of evaluation of the event.

6.6 Dose Modification (Escalation/Titration/Other)

Adverse events (both nonserious and serious) associated with V937 and pembrolizumab exposure may represent an immunologic etiology. These AEs may occur shortly after the first dose or several months after the last dose of treatment.

The CTCAE Version 5.0 must be used to grade the severity of AEs. The investigator may attribute each toxicity event to V937 alone, to pembrolizumab alone, or to the combination, and modify the dose according to [Table 9](#). Although the investigator may attribute an AE to V937 alone, pembrolizumab must be held for AEs as indicated in [Table 9](#), regardless of attribution.

Reduction or holding of 1 agent and not the other agent is appropriate if, in the opinion of the investigator, the toxicity is clearly related to 1 of the study interventions. For example, in combination, if V937 is held due to an AE attributed to that drug, then pembrolizumab may continue to be administered, and vice versa. Appropriate documentation is required regarding to which drug the investigator is attributing the AE. If, in the opinion of the investigator, the toxicity is related to the combination of 2 agents, then both drugs should be held according to recommended dose modifications.

Pembrolizumab or V937 may be interrupted for situations other than treatment-related AEs such as medical / surgical events or logistical reasons not related to study therapy. Participants should be placed back on study therapy within 3 weeks of the scheduled interruption, unless otherwise discussed with the Sponsor. The reason for interruption should be documented in the participant's study record.

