6.6.1 Dose Modification for V937

The most common drug-related adverse reactions seen with V937 treatment continue to be fatigue, chills, pyrexia and influenza-like illness. These events are mainly Grade 1 or 2 in severity, transient, and easily managed.

In addition, a group of treatment-related AEs is specific to studies where V937 is delivered by ITu administration. This includes injection site pain, injection site erythema, injection site reaction, injection site pruritis, injection site discharge and injection site edema. These AEs are associated with the intralesional procedure, and have not been reported when V937 has been given by the IV or intravesicular route. These symptoms are limited to being mild (Grade 1) in severity.

As common practice, anti-inflammatory or anti-allergic agents, such as acetaminophen or ibuprofen, should be initiated if Grade 2 fever, chill, or site injection reaction occurs. Permanently discontinue V937 if these Grade 2 AEs reoccur in the same participants or are >Grade 2. For infusion reaction related to IV administered V937, please refer to [Table 10](#) for guidance. For other instances in which dose interruption(s) may be required, discuss with Sponsor.

Pembrolizumab treatment will be modified for the AEs described in Section 6.6.2.

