6.7 Intervention After the End of the Study

Due to discontinuation of V937-011, participants who have completed or discontinued V937 treatment and are only receiving pembrolizumab may be enrolled in a pembrolizumab extension study, if available, to continue pembrolizumab monotherapy for up to 35 cycles from first pembrolizumab dose on V937-011 and to be monitored per the extension study as appropriate.

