8.1.10.1 Timing of Dose Administration

In all arms of the study, pembrolizumab will be administered on Day 8 of Cycle 1 (28-day cycle) and on Day 1 of all subsequent cycles. V937 will be administered either IV (Arm 1) or ITu (Arm 2) on Days 1, 3, 5, and 8 of Cycle 1 (28 days); on Day 8 of Cycle 1, V937 will be administered 0.5 to 4 hours after a 200-mg dose of pembrolizumab infused over 30 minutes. For Cycles 2-8, V937 will be administered IV (Arm 1) or ITu (Arm 2) on Day 1 of each 21-day cycle, 0.5 to 4 hours after a 200-mg dose of pembrolizumab infused over 30 minutes. Each participant may undergo up to 11 administrations of V937 and may continue treatment with pembrolizumab for up to a total of 35 cycles (approximately 2 years).

In Cycle 1, for the first 4 doses of V937 in Arms 1 and 2, a window of 24 hours for dosing will be allowed to accommodate weekends. In Cycle 2, study intervention may be administered up to 3 days after the scheduled Day 1. Beginning in Cycle 3, study intervention may be administered up to 3 days before or after the scheduled Day 1.

Dosing interruptions are permitted in the case of medical/surgical events or logistical reasons that are not related to study therapy (eg, elective surgery, unrelated medical events, participant vacation, and/or holidays). Participants should be placed back on study therapy within 3 weeks of the scheduled interruption, unless otherwise discussed with the Sponsor Medical Monitor or designee. The reason for interruption should be documented in the participant's study record.

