6.6.2 Dose Modification for Pembrolizumab

The following information provides additional irAEs and related details to what is stated in Table 9.

irAEs	Toxicity grade (CTCAE v5.0)	Action with pembrolizumab
Endocrinopathies	Grade 2 adrenal insufficiency and hypophysitis	Withhold treatment until controlled by hormone replacement
	Grades 3 or 4 adrenal insufficiency or symptomatic hypophysitis	Withhold until adverse reactions recover to Grades 0-1 ^a
	Type 1 diabetes associated with Grade ≥ 3 hyperglycemia (glucose >250 mg/dL or >13.9 mmol/L) or associated with ketoacidosis	For patients with Grade 3 or Grade 4 endocrinopathies that improved to Grade 2 or lower and are controlled with hormone replacement, if indicated, continuation of pembrolizumab may be considered after corticosteroid taper, if needed. Otherwise treatment should be discontinued.
	Hyperthyroidism Grade ≥ 3	
	Hypothyroidism	Hypothyroidism may be managed with replacement therapy without treatment interruption.

irAEs	Toxicity grade (CTCAE v5.0)	Action with pembrolizumab
Hepatitis	Grade 2 with aspartate aminotransferase (AST) or alanine aminotransferase (ALT) >3 to 5 times ULN or total bilirubin >1.5 to 3 times ULN	Withhold until adverse reactions recover to Grades 0-1 ^a
	Grade ≥3 with AST or ALT >5 times ULN or total bilirubin >3 times ULN	Permanently discontinue
	In case of liver metastasis with baseline Grade 2 elevation of AST or ALT, hepatitis with AST or ALT increases ≥50% and lasts ≥1week	Permanently discontinue
Skin reactions	Grade 3 or suspected Stevens-Johnson syndrome (SJS) or toxic epidermal necrolysis (TEN)	Withhold until adverse reactions recover to Grades 0-1 ^a
	Grade 4 or confirmed SJS or TEN	Permanently discontinue
^a If treatment-related toxicity does not resolve to Grades 0-1 within 12 weeks after last dose of pembrolizumab, or if corticosteroid dosing cannot be reduced to ≤10 mg prednisone or equivalent per day within 12 weeks, pembrolizumab should be permanently discontinued.		

Italy

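### Section 6.6 lets pembrolizumab continue when V937 is held for a V937-attributed event, with no exception for the Table 9 events that require a pembrolizumab hold whatever the attribution

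*Combined protocol and SAP*

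**What the plan says.** Section 6.6 opens with the premise that "Adverse events (both nonserious and serious) associated with V937 and pembrolizumab exposure may represent an immunologic etiology". Its second paragraph then sets the rule: "Although the investigator may attribute an AE to V937 alone, pembrolizumab must be held for AEs as indicated in" Table 9, irrespective of the agent to which the event is attributed.

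The third paragraph takes a different basis. It accepts holding one agent alone when the investigator considers the toxicity clearly related to that agent, and gives the example "if V937 is held due to an AE attributed to that drug, then pembrolizumab may continue to be administered, and vice versa". It asks for both drugs to be held when the toxicity is attributed to the combination.

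Section 6.6.1 describes the usual V937 reactions: "The most common drug-related adverse reactions seen with V937 treatment continue to be fatigue, chills, pyrexia and influenza-like illness", with injection-site events for the intratumoral route. It sends pembrolizumab modification to Section 6.6.2. Section 6.5.3.2, on supportive care, says: "The treatment guidelines are intended to be applied when the investigator determines the events to be related to pembrolizumab". It excuses the investigator from the guidance if the event is not related to pembrolizumab, then refers to Table 9 for dose modification as well as supportive care.

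**The concern.** The example in the third paragraph is the case that the second paragraph has just regulated: an event attributed to V937 alone. One paragraph says pembrolizumab must be held if the event is in Table 9. The other says it may continue and mentions no Table 9 exception. Section 6.5.3.2 makes the permissive reading easier, because it ties the guidance to pembrolizumab-relatedness.

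The stake is patient safety. A site in Arm 1 or Arm 2 that follows the third paragraph literally could give pembrolizumab during an event for which Table 9 requires it to be withheld. Grade 1 myocarditis shows why this matters: at the next grade Table 9 already requires permanent discontinuation. Efficacy and safety estimates are not at issue.

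**Working it through.** The plan has no figure of its own to reproduce. The check is a comparison of texts, followed by counts that bound the reach of the problem.

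**1. The two rules on the same case.** Take Grade 2 pneumonitis attributed to V937 alone.
- Second paragraph of 6.6 with Table 9: pembrolizumab must be held.
- Third paragraph of 6.6: V937 is held and pembrolizumab may continue.

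Sections 6.6.1 and 6.6.2 and Table 9 with its footnotes state no order of precedence.

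**2. Is such a case within the section?** Yes. The opening sentence of 6.6 allows that V937-associated events may be immunologic, and the second paragraph expressly allows attribution to V937 alone. The third paragraph is not confined to events outside Table 9. It has no such limit, and its combination rule refers to the recommended dose modifications.

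**3. Table 9 rows by action** (one row per grade entry):

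| Action on pembrolizumab | Rows | Count |
|---|---|---|
| Withhold | pneumonitis G2; diarrhea/colitis G2-3; AST/ALT/bilirubin G2; T1DM/hyperglycemia; hypophysitis G2; nephritis G2; neurological G2; myocarditis G1; suspected SJS/TEN/DRESS; other irAE, persistent G2 | 10 |
| Withhold or discontinue | hypophysitis G3-4; hyperthyroidism G3-4; other irAE G3 | 3 |
| Permanently discontinue | pneumonitis; colitis; liver; nephritis; neurological; myocarditis; confirmed SJS/TEN/DRESS; other irAE | 8 |
| Continue | hyperthyroidism G2; hypothyroidism G2-4 | 2 |

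Total: 10 + 3 + 8 + 2 = 23.

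- The 2 continue rows raise no conflict.
- The 8 permanent-discontinuation rows are also covered by Section 7.1, which requires discontinuation for any study-intervention-related toxicity so specified.
- Rows reached by the literal permission: 10 + 3 = 13.

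Of the 13, those that can contain a Grade 3 or higher event are diarrhea/colitis G2-3, T1DM/hyperglycemia, hypophysitis G3-4, hyperthyroidism G3-4 and other irAE G3, which is 5. The remaining 13 - 5 = 8 are Grade 1 or 2 rows or, for suspected SJS/TEN/DRESS, carry no grade. The documents give no rate for those 8.

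**4. Who and when.**
- Participants: Arms 1 and 2 of a 1:1:1 allocation, 2 × 135/3 = 90 planned, possibly fewer after early termination.
- Doses: Section 8.1.10.1 states that "Each participant may undergo up to 11 administrations of V937 and may continue treatment with pembrolizumab for up to a total of 35 cycles". On the planned schedule V937 and pembrolizumab overlap at Cycle 1 Day 8 and Day 1 of Cycles 2 to 8: 1 + 7 = 8 pembrolizumab doses, and 8/35 = 22.9%.

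**5. Does early termination remove the issue?** No. Under Section 6.7, "participants who have completed or discontinued V937 treatment and are only receiving pembrolizumab may be enrolled in a pembrolizumab extension study". Anyone still receiving V937 does not meet that condition and remains under this text.

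**The case against.** The strongest reply is that the exception is already in the section. The second paragraph is mandatory, names the exact scenario, and stands directly before the sentence criticised. The third is a general permission, limited to toxicity clearly related to one agent, and it has its own work to do: fever, chills, influenza-like illness and injection-site reactions are not named Table 9 rows. Both paragraphs then have effect. Section 6.6.1 also sends pembrolizumab modification to Section 6.6.2 without an attribution condition, and Section 10.3.5 steers causality towards the combination, for which both drugs are held. On this view the 13 rows are reached only by ignoring an adjacent mandatory sentence, and the harm is hypothetical.

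Much of this stands. The mandatory reading is the better one, the row count measures the reach of the wording and not risk, and the consequence may be nil. Section 6.5.3.2 is weaker support, since it sits under supportive care. What remains is that the protocol states neither the precedence nor a restriction of the third paragraph to events outside Table 9. A mandatory hold should not depend on which of two neighbouring paragraphs a site applies.

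A further objection is that the proposed change leaves open whether V937 may continue during a Table 9 hold, given that the table's action column mentions immuno-oncology combinations. That is a separate clinical question, which the change neither settles nor worsens.

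**Conclusion.** The inconsistency holds and is minor. Read literally, the third paragraph of 6.6 permits pembrolizumab during events for which the second paragraph requires a hold, across 13 of the 23 Table 9 grade rows. It is bounded by at most 90 planned participants and at most 8 of 35 pembrolizumab doses each. The number affected is likely small, may be zero, and cannot be estimated from the documents.

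The conclusion assumes that a site could attribute a Table 9 event to V937 alone, which 6.6 expressly allows, and that a participant is still within the V937 dosing period. The documents do not show how many, if any, are.

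**What to change.** In the third paragraph of Section 6.6, directly after the permission to continue pembrolizumab, add: *except for AEs for which Table 9 (as supplemented by Appendix 7) directs that pembrolizumab be withheld or discontinued, for which pembrolizumab must be held or discontinued regardless of attribution*. The reference to Appendix 7 is needed because the France and Italy entries add to the table: "The following information provides additional irAEs and related details to what is stated in Table 9". Leave the converse permission, to continue V937 when pembrolizumab is held, as it is.

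In Section 6.5.3.2, state that the condition of relatedness to pembrolizumab applies to corticosteroid and other supportive treatment only, and not to the hold required by Section 6.6.

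The cost is one clause and one sentence. Single-agent holding for the common V937 reactions outside the Table 9 rows is kept, and V937 dosing rules, data collection and analyses do not change.
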